5.2 Roll-in

- **Roll-In Analysis Set:** The Roll-In analysis set will include all subjects who are enrolled in the roll-in phase and have undergone ablation with the IRE ablation system.

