### **8.1.2 Wave II: Roll-In Subjects**

New devices often require operators to scale a learning curve. The inclusion of a roll-in phase in the study will allow learning for the operators, and an evaluation of safety and effectiveness of the device that is not diminished by the early learning curve. In addition to a requirement for IRE ablation System training for ablating physicians, further experience within the context of this clinical investigational plan will serve to generate a clearer perspective of the effectiveness of the IRE ablation System in treating PAF subjects. Therefore, as of Wave II, up to the first 3 subjects (operator dependent based on criteria defined per training charter) treated by an ablating physician with the study catheter will be prospectively assigned as roll-in subjects to minimize the learning curve effect. To allow for a wide range of physician skill level, up to three physicians per site will be able to participate. Because roll-in subjects are at the physician level, some physicians at a site may complete their roll-in subjects and move to the main study phase while other physicians at the site are still in the roll-in phase. A subject who is excluded or discontinued will not count toward the

roll-in subjects. Roll-in subjects will be followed for 12 months post index procedure. The results from the roll-in phase will be analyzed and presented separately from the main study phase.

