### 20.3.2 Wave II Analysis Sets

- **Modified Intent-To-Treat (mITT-Wave II) Analysis Set:** The mITT-Wave II analysis set will consist of enrolled Wave II main study phase subjects who meet eligibility criteria and have had insertion of the study catheter—Subjects in this analysis set who are discontinued due to:
  - study catheter related reasons will be considered acute effectiveness failures
  - non-study catheter related reasons (other equipment, pump, anatomy that precludes treatment with the study catheter or commercially available catheter) will be excluded from the effectiveness analysis.
- **Full Analysis set (FAS-Wave II):** The FAS-Wave II Analysis Set will consist of all enrolled Wave II main study phase subjects who have had insertion of the study catheter (with or without delivery of PFA).
- **Per Protocol (PP-Wave II) Analysis Set:** The PP-Wave II analysis set will consist of Wave II main study phase subjects who satisfy the following criteria:
  - are enrolled and without major protocol deviations that would affect the integrity of the data
  - have undergone ablation (PFA) with the study catheter
  - are treated for the study-related arrhythmia
  - did not require the use of a non-study catheter for Pulmonary Vein Isolation (PVI)
  - did not require ablations outside the PV region
- **Roll-In Analysis Set:** The Roll-In analysis set will include all subjects who are enrolled in the roll-in phase. All endpoints will be analyzed for the roll-in analysis set separately.

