5 ANALYSIS SETS

5.1 Main Phase

For the analysis of study endpoints, the analysis sets defined in the following will be used:

- **Full Analysis Set (FAS):** The FAS will consist of all enrolled subjects who have had insertion of the study catheter (with or without delivery of pulse field ablation [PFA]).
- **Modified Intent-To-Treat (mITT) Analysis Set:** The mITT analysis set will consist of enrolled subjects who have had insertion of the study catheter and meet eligibility criteria.

- **Per Protocol (PP) Analysis Set:** The PP analysis set will consist of all enrolled subjects who satisfy the following criteria:
 - Have undergone ablation with the IRE ablation system.
 - Are treated for the study-related arrhythmia.
 - Are without major protocol deviations that would affect the scientific integrity of the primary safety and effectiveness data, including but not limited to the following:
 - Subjects found not meeting eligibility criteria
 - Use of the IRE ablation modality to ablate outside the PV region
 - Failure to check for entrance block for each targeted PV after adenosine/isoproterenol challenge

Eligible subjects treated with commercially available catheters for non-PV triggers that may arise during the index procedure or during repeat procedures occurring during the blanking period will be followed for the full duration of follow-up and will be evaluable for all endpoints in order to preclude potential bias that would arise from exclusion of these subject profiles from endpoint estimates.

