7.2 Subject Disposition

Disposition and accountability of the study subjects will be summarized descriptively for the following subject categories:

- **Enrolled Subjects:** Patients who sign the informed consent form (ICF).
- **Excluded Subjects:** Subjects who are enrolled but never undergo insertion of the study catheter. Excluded subjects will be subjected to safety event reporting between ICF signature and date of exclusion. Subjects who signed the ICF but are found to be ineligible prior to insertion of the catheter are also considered as excluded.
- **Discontinued Subjects:** Subjects in whom the catheter is inserted but do not undergo ablation (i.e., no energy is delivered with the study catheter).
 - Discontinued subjects will remain in follow-up for 3-months post catheter insertion.
 - If an SAE is reported for a discontinued subject, the subject will be followed until event resolution (with or without sequelae), stabilization, or until the event is adequately explained.
- **Lost to Follow-up Subjects:** Subjects in whom the catheter is inserted for which contact is lost after most recent visit (despite 3 documented attempts to contact the subject).
- **Withdrawn / Early Termination Subjects:** Subjects who withdraw consent for study participation or are withdrawn by the investigator, are terminated from the study prior to completion of all follow-up visits.
- **Completed Subjects:** Enrolled subjects who have not been excluded, discontinued, withdrawn, terminated early, or lost-to-follow-up from the study prior to the final study visit.

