7.7 Analysis of Roll-In Subjects

Descriptive statistics will be presented for all Wave II endpoints for subjects in the Roll-in analysis set, separately.

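### SAP 5.2 leaves a roll-in subject with the catheter inserted but no PFA delivered out of every SAP endpoint table, so the descriptive roll-in safety rate could be understated

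*SAP*

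**What the plan says.** The two documents define the Roll-In set differently.

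- Protocol 20.3.2: "The Roll-In analysis set will include all subjects who are enrolled in the roll-in phase".
- Wave II SAP 5.2: "all subjects who are enrolled in the roll-in phase and have undergone ablation with the IRE ablation system". The SAP gives no reason for the added condition.

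SAP 7.7 then makes this set the only vehicle for roll-in results: "Descriptive statistics will be presented for all Wave II endpoints for subjects in the Roll-in analysis set, separately".

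The subject at issue belongs to the discontinued category in SAP 7.2: "Subjects in whom the catheter is inserted but do not undergo ablation (i.e., no energy is delivered with the study catheter". Such subjects stay in follow-up for 3 months after insertion (Protocol 10.3, SAP 7.2).

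For the main phase, safety is based on insertion. SAP 5.1, headed Main Phase, defines the FAS as "all enrolled subjects who have had insertion of the study catheter (with or without delivery of pulse field ablation [PFA"]. Protocol 20.3.2 gives it as "all enrolled Wave II main study phase subjects who have had insertion of the study catheter (with or without delivery of PFA"), and the mITT set as "enrolled Wave II main study phase subjects who meet eligibility criteria and have had insertion of the study catheter". Roll-in data are analysed separately and stay outside the primary hypothesis tests (Protocol 8.2).

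**The concern.** The roll-in phase, with up to 180 subjects, exists because operators are learning a new device (Protocol 8.1.2). Its safety summary is where a reader would look for the risk of first use.

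Harm before any energy is delivered is foreseeable on the plan's own terms. Protocol 6.4.1 lists catheter manipulation as a cause of perforation. Protocol 14.2.2.2 requires a left atrial map before ablation and allows the study catheter to be used for it in Wave II. The primary safety endpoint runs from the initial mapping and ablation procedure (Protocol 8.2.1, SAP 7.4.1).

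If a tamponade during mapping ends the procedure, an eligible main-phase subject counts in the primary safety rate. The same event in a roll-in subject reaches no SAP endpoint table. Under SAP 5.2, membership of the set can thus depend on the outcome that the set is meant to measure.

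**Working it through.** **Step 1: trace the subject.** Take a roll-in subject with the study catheter inserted and no PFA delivered.

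| Set | Included? | Reason |
|---|---|---|
| FAS | No | SAP 5.1 is headed Main Phase; Protocol 20.3.2 names main-phase subjects |
| mITT | No | Same; SAP Appendix I, 10.3 also counts mITT enrolment without roll-ins |
| PP | No | Requires ablation, and is a main-phase set |
| Roll-In (SAP 5.2) | No | Requires ablation |
| Roll-In (Protocol 20.3.2) | Yes | Enrolment in the phase is enough |
| Safety (Protocol 20.4.6) | Unknown | Named there, defined in neither document |

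SAP 7.6.2 analyses the additional safety endpoints in FAS and mITT, and SAP 7.7 covers roll-ins through the Roll-In set. No SAP endpoint table therefore includes this subject.

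**Step 2: compare with the other cohorts.** The Wave I SAP also defines its FAS and mITT sets by insertion and reports safety in them. Its sample-size statement assumes 35 subjects with the catheter inserted: 1 − 0.93^35 = 0.921, which agrees with its stated figure of more than 90%. Among the safety summaries, only the roll-in one is conditional on energy delivery.

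**Step 3: size.** The documents state no figure for this point and no rate of insertion without ablation, so what follows is illustration.

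- N = 180 inserted roll-in subjects. This is the stated maximum; the cohort may be smaller (SAP section 1).
- E = 13 PAEs among all inserted subjects. This is assumed: 13/180 = 7.22%, close to the 7% planning rate.
- d = subjects dropped (inserted, no PFA), of whom x had a PAE. Both are assumed.

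Rate under SAP 5.2 = (E − x)/(N − d). Rate in all inserted subjects = E/N = 7.22%.

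| d | x = 0 | x = 1 | x = 2 | x = 3 |
|---|---|---|---|---|
| 1 | 13/179 = 7.26% | 12/179 = 6.70% | – | – |
| 5 | 13/175 = 7.43% | 12/175 = 6.86% | 11/175 = 6.29% | 10/175 = 5.71% |
| 9 | 13/171 = 7.60% | 12/171 = 7.02% | 11/171 = 6.43% | 10/171 = 5.85% |
| 14 | 13/166 = 7.83% | 12/166 = 7.23% | 11/166 = 6.63% | 10/166 = 6.02% |

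**Step 4: direction.** The reported rate is too low when (13 − x)/(180 − d) < 13/180, that is, when x/d > 13/180 = 7.2%. With x = 1 this needs d < 180/13 = 13.8, so 13 or fewer dropped subjects. If no dropped subject was injured, the reported rate is slightly too high.

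**The case against.** **The events are not lost to oversight.** Adverse events are collected from consent onward and reported to the sponsor (Protocol 15.4.1). The CEC adjudicates primary safety events and the DMC reviews safety data for Wave II (Protocol 6.4.2, SAP section 8). Discontinued subjects appear in the disposition summary (SAP 7.2). This stands. A reader might infer that such an injury would go unseen, but the documents support only the narrower statement that no SAP endpoint table holds it.

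**The direction of the error is not fixed.** This also stands. A reader might infer that the roll-in rate is biased low as a matter of fact. Step 4 shows that this requires the injured share of dropped subjects to exceed the overall rate, and no document gives that share.

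**The SAP's FAS wording might include roll-ins.** Read alone, SAP 5.1 does not repeat the main-phase restriction. Its heading, Protocol 20.3.2 and Appendix I, 10.3 rule that reading out.

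**Protocol 8.1.2 might settle the matter.** It says: "A subject who is excluded or discontinued will not count toward the" roll-in subjects. In a paragraph on each physician's first cases, this reads as a quota rule. Even read as a classification, it places the subject in no other set. It neither creates nor closes the gap.

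**Operators are experienced, and the window may be short.** Protocol 6.4.2 and 18.1.1 call for investigators experienced in mapping and AF ablation, and mapping may be done without the study catheter. Both facts limit how often this would arise. They also mean that the documents do not support blaming inexperienced operators. In addition, a complication before study-catheter insertion makes the subject excluded (Protocol 10.3), and that subject is outside the main-phase FAS and mITT as well. That part is not specific to roll-in.

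**Conclusion.** The mismatch between SAP 5.2 and Protocol 20.3.2 is certain, and so is its consequence for the SAP's endpoint tables. Its numerical effect is unknown. With 180 inserted subjects, 13 PAEs and five dropped, the reported rate moves from the full rate of 7.2% to 7.4%, 6.9% or 5.7% for zero, one or three injured among the five. These counts are assumptions. In a smaller roll-in cohort each lost event weighs more: 1/60 = 1.7 points against 1/180 = 0.6 points, where 60 is only an example.

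Two further inferences should be resisted. The primary safety conclusion is not affected: roll-in data are descriptive and do not enter the 14% test, the sample-size rule or the early-success decision. Nor does the gap invalidate a planned contrast between roll-in and main-phase subjects, because none is planned. It would matter only to a reader who set the two rates side by side.

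The point is still worth acting on. The rule as written lets a complication decide whether the subject is analysed, in the cohort set up to absorb the learning curve.

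**What to change.** In Wave II SAP 5.2, add a roll-in safety set: all roll-in subjects who had the study catheter inserted, with or without PFA, mirroring the FAS. Report PAEs, SAEs and SADEs in it, and amend SAP 7.7 to name it. Keep the ablated-only set for effectiveness and procedural summaries.

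Reconcile this with Protocol 20.3.2. Enrolment there means signing consent (Protocol 10.3), so the protocol's Roll-In set is wider still and includes subjects who never had the catheter inserted; the SAP should state that the safety set starts at insertion. Define or delete the Safety set named in Protocol 20.4.6.

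The cost is a short SAP amendment and no new data, since discontinued subjects are already followed for 3 months with adverse events recorded. The downside is that the roll-in safety rate may be slightly less favourable.

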6 SAMPLE SIZE JUSTIFICATION

A Bayesian adaptive design will be utilized to select the final sample size of the trial. Two sample size selection interim analyses will be performed based on the primary effectiveness endpoint. The first sample size selection interim analysis will be performed when enrollment in the mITT analysis set reaches 180. From simulations with realistic enrollment scenario, at this first interim timing, it is expected that about 30% of subjects will have between 3- and 6-months follow-up, about 18% of subjects will have between 6- and 9-months follow-up, and about 2% of subjects will have between 9- and 12-months follow-up. Predictive probabilities for trial success for the effectiveness endpoint will be used to determine whether the sample size of 180 will be sufficient or if the trial will continue enrollment. If the predictive probability with the current sample size of 180 is greater than 90%, or if the predictive probability with the maximum sample size of 330 is less than 2.5%, then enrollment will be stopped.

In case of continuation of enrollment, the second sample size interim analysis will be performed when enrollment in the mITT analysis set reaches 255. From simulations with realistic enrollment scenario, at this second interim timing, it is expected that about 27% of subjects will have between 3- and 6-months follow-up, about 27% of subjects will have between 6- and 9-months follow-up, and about 19% of subjects will have between 9- and 12-months follow-up. Predictive probabilities for trial success for the effectiveness endpoint will be used to determine whether the sample size of 255 will be sufficient or if the trial will continue to the full sample of 330. If the predictive probability with the current sample size of 255 is greater than 90%, or if the predictive probability with the maximum sample size of 330 is less than 2.5%, then enrollment will be stopped.

Under the assumption of 7% and 65% rates for the primary safety and effectiveness endpoints respectively, the study will be adequately powered for trial success (over 80%). The highest type I error rates were estimated in the following two scenarios: 1) the true primary safety rate was on the decision boundary (i.e., equal to 14%) and the device was assumed to be very effective, and 2) the true primary effectiveness rate was on the decision boundary (i.e., equal to 50%) and the device was assumed to be very safe. In both scenarios, the overall type I error for claiming success for both safety and effectiveness is controlled at 2.5%. For details of the simulation results of power and type I error, please refer to Appendix I - Adaptive Design Simulation Report.

7 STATISTICAL ANALYSIS METHODS

7.1 General Conventions

Standard descriptive summaries for continuous data include the number of observations with data, mean, standard deviation, median, 25th percentile, 75th percentile, minimum, and maximum values. For categorical data, the count and percent will be provided. Percentages will be based on the number of subjects without missing data.

7.2 Subject Disposition

Disposition and accountability of the study subjects will be summarized descriptively for the following subject categories:

- **Enrolled Subjects:** Patients who sign the informed consent form (ICF).
- **Excluded Subjects:** Subjects who are enrolled but never undergo insertion of the study catheter. Excluded subjects will be subjected to safety event reporting between ICF signature and date of exclusion. Subjects who signed the ICF but are found to be ineligible prior to insertion of the catheter are also considered as excluded.
- **Discontinued Subjects:** Subjects in whom the catheter is inserted but do not undergo ablation (i.e., no energy is delivered with the study catheter).
 - Discontinued subjects will remain in follow-up for 3-months post catheter insertion.
 - If an SAE is reported for a discontinued subject, the subject will be followed until event resolution (with or without sequelae), stabilization, or until the event is adequately explained.
- **Lost to Follow-up Subjects:** Subjects in whom the catheter is inserted for which contact is lost after most recent visit (despite 3 documented attempts to contact the subject).
- **Withdrawn / Early Termination Subjects:** Subjects who withdraw consent for study participation or are withdrawn by the investigator, are terminated from the study prior to completion of all follow-up visits.
- **Completed Subjects:** Enrolled subjects who have not been excluded, discontinued, withdrawn, terminated early, or lost-to-follow-up from the study prior to the final study visit.

7.3 Demographic and Baseline Characteristics

Subject demographics, medical history, previously failed antiarrhythmic drugs (AADs), active AAD use at baseline, and other baseline data will be summarized descriptively for subjects in the FAS, mITT, PP, and Roll-in analysis sets.

7.4 Analysis of Primary Endpoints

A single interim analysis is planned for an early success evaluation. The interim analysis will be performed when 30 subjects complete full 12 months of follow-up and all subjects complete 3 months of follow-up in the mITT analysis set. If early success is achieved, an early success interim analysis Clinical Study Report (CSR) will be compiled to present the results of the study success. If early success is not achieved, then the final primary endpoint analyses will be performed at the end of the study using the full follow-up data.

7.4.1 Primary Safety Endpoint

The primary safety endpoint is the occurrence of any PAE within 7 days of the initial mapping and ablation procedure. The definition of PAE can be found in section 8.2.1 of the study protocol.

The PAE rate will be compared against a performance goal of 14% by testing the following hypotheses:

$$H_0: p_s \geq 0.14 \quad vs \quad H_A: p_s < 0.14,$$

Where p_s is the PAE rate. The mITT analysis set will be the primary analysis set for the early success interim analysis and final analysis of primary safety endpoint.

7.4.1.1 Early Success Interim Analysis of Primary Safety Endpoint

The primary safety outcome for all subjects will be known at the time of the interim analysis and will be used for hypothesis testing. Notably, primary adverse events only occur within a 3-month window of the procedure by definition (with the exception of a procedure or device related death, pulmonary vein stenosis, and atrio-esophageal fistula) which will result in nearly identical hypothesis tests at the interim and final analyses.

At the time of the early success interim analysis, the primary safety endpoint will be met if:

$$\Pr(p_s < 0.14 | y, n) > 0.975$$

where p_s is the PAE rate. A beta-binomial model with a non-informative uniform prior Beta (1,1) will be used for the safety rate. If the posterior probability of the safety rate being less than 14% is greater than 0.975 then the study will be considered to have demonstrated safety of the device at the early success interim analysis.

To investigate the robustness of the analysis result, the following sensitivity analyses will be performed in the FAS and mITT analysis sets unless otherwise noted at the time of the early success interim analysis with available data:

- **Sensitivity to Analysis Set**

The primary safety endpoint will be analyzed in the FAS as a sensitivity analysis.

- **Snap-Shot Binomial Analysis**

The number and percentage of subjects with primary safety events will be presented along with one-sided 97.5% exact binomial upper confidence bounds. Subjects with missing outcomes will be excluded from the analysis. Missing outcomes of primary safety endpoints is defined in Section 7.4.3.

- **Best-case Scenario**

The point estimate for the PAE rate will be estimated by treating subjects with missing primary safety outcomes as free from primary safety events.

- **Worst-case Scenario**

The point estimate for the PAE rate will be estimated by treating subjects with missing primary safety outcomes as failures.

- **Tipping Point Analysis**

Tipping point analysis will be performed for the primary safety endpoint to assess the impact of missing outcomes on the safety conclusion. The posterior distribution will be updated each time treating a subject with a missing outcome as failure to evaluate whether a tipping point is identified.

7.4.1.2 Final Analysis of Primary Safety Endpoint

If early success is not achieved, then the final primary safety endpoint analysis will be performed at the end of the study.

The final analysis for the primary safety endpoint will use a beta-binomial model with a non-informative uniform prior Beta (1,1). At the time of the final analysis, the primary safety endpoint will be considered as success if:

$$\Pr(p_S < 0.14|y, n) > 0.975$$

where p_s is the PAE rate. If the posterior probability of the safety rate being less than 14% is greater than 0.975 then the study will be considered to have demonstrated safety of the device.

To investigate the robustness of the analysis result, the following sensitivity analyses will be performed in the FAS and mITT analysis sets unless otherwise noted at the time of the final safety analysis:

- **Sensitivity to Analysis Set**

The primary safety endpoint will be analyzed in the FAS as a sensitivity analysis.

- **Snap-Shot Binomial Analysis**

The number and percentage of subjects with primary safety events will be presented along with one-sided 97.5% exact binomial upper confidence bounds. Subjects with missing outcomes will be excluded from the analysis. Missing outcomes of primary safety endpoints is defined in Section 7.4.3.

- **Best-case Scenario**

The point estimate for the PAE rate will be estimated by treating subjects with missing primary safety outcomes as free from primary safety events.

- **Worst-case Scenario**

The point estimate for the PAE rate will be estimated by treating subjects with missing primary safety outcomes as failures.

- **Tipping Point Analysis**

Tipping point analysis will be performed for the primary safety endpoint to assess the impact of missing outcomes on the safety conclusion. The posterior distribution will be updated each time treating a subject with a missing outcome as failure to evaluate whether a tipping point is identified.

If early success is achieved, the primary safety endpoint and associated sensitivity analyses based on full 12-month follow-up data will be summarized descriptively.

